5.3.9 Exposure to Treatment

Exposure to treatment

DB period: exposure will be calculated as the number of days from the date of the first dose (as recorded in Trial Drug part of CRF) to the date of Visit 8 or until date of discontinuation of double-blind Treatment, whichever occurs first.

FU period: exposure for patients enrolled under protocol versions 1 through 3 will be calculated from start and stop dates in the Concomitant Medication part of the CRF. Exposure for patients enrolled under protocol versions 4 through 5 will be calculated from the date of Visit 8 to the date of Visit 11 or until discontinuation of treatment.

Duration of exposure will be summarized/tabulated by treatment group using descriptive statistics, including the number and proportion of subjects exposed in defined intervals (at least one day to 4 weeks; more than 4 to 8 weeks; more than 8 to 12 weeks; more than 12 to 16 weeks; more than 16 to 20 weeks, and more than 20 to 24 weeks in the DB period, and similarly but in 4-weekly intervals in the FU period).

Exposure as defined above will also be listed by site and subject (including information on premature withdrawal from trial/discontinuation of treatment where relevant).

Compliance

Compliance will be calculated as the total number of empty vials returned divided by the total number of days in the trial.

Compliance will be summarized/tabulated by treatment group using descriptive statistics, including the number and proportion of subjects in defined compliance intervals (90% or more; 80% or more; 70% or more; 50 to 69%; 49% or less). Compliance will also be listed by site and subject (including information on premature withdrawal from trial/discontinuation of treatment where relevant).

Additional data that will only be listed include: answer to CRF question 'Medication taken according to instruction' and nebulizer tracking data (not part of the CRF and only available in a subgroup of subjects).

Rescue medication

Administration of any rescue medication, the type of, reason for, and the corresponding start time and time period of rescue medication will be listed separately.

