7.2.1.9 Week 24 (Visit 8)

TIME WINDOW:

168 days (± 7 days) after Randomisation (Visit 2)

The CT scan can be performed seven days prior to or after Week 24 (Visit 8)

ACTIVITIES AND ASSESSMENTS:

At Week 24 (Visit 8), the following activities and assessments will be performed:

- Concomitant medication (*Section 10.3.3*)
- Physical examination (*Section 10.4.3*)
- Vital signs (*Section 10.4.4*)
- (A-a)DO₂ and PaO₂ (*Section 10.1.1*)
- Lung function tests (*Section 10.1.2*)
- 6MWT (*Section 10.1.3*)
- Dyspnoea score (*Section 10.1.4*)
- Cough scores (*Section 10.1.5*)
- CT (*Section 10.1.6*)
- QoL score (*Section 10.1.7*)
- DSS (*Section 10.1.8*)
- ECG (*Section 10.4.5*)
- Serum pregnancy test (*Section 10.5*)
- Laboratory safety assessments (haematology and clinical chemistry), (*Section 10.4.6*)
- Biomarkers and anti-drug antibodies prior to administration of trial drug in clinic (*Section 10.1.9*)
- AEs (*Section 10.4.2*)
- Subject Diary Card (*Section 10.4.2*)
- Treatment compliance (*Section 9.5*)
- Administration of trial drug at the site (*Section 9.1.5*)
- Dispense trial drug (*Section 9.1.4*)

7.2.1.10 4-Week Telephone Follow-up (Visit 9)

TIME WINDOW:

28 days (±3 days) after Week 24 (Visit 8).

ACTIVITIES AND ASSESSMENTS:

At 4-Week Telephone Follow-up (Visit 9), the following activities and assessments will be performed:

- AEs (*Section 10.4.2*)
- Medication/therapy for aPAP (*Section 10.3.3*)

7.2.1.11 12-Week Follow-up (Visit 10)

TIME WINDOW:

84 days (±14 days) after Week 24 (Visit 8)

ACTIVITIES AND ASSESSMENTS:

At 12-week Follow-up (Visit 10), the following activities and assessments will be performed:

- Medication/therapy for aPAP (*Section 10.3.3*)

- (A-a)DO₂ and PaO₂ (*Section 10.1.1*)
- Lung function tests (*Section 10.1.2*)
- 6MWT (*Section 10.1.3*)
- Dyspnoea score (*Section 10.1.4*)
- Cough scores (*Section 10.1.5*)
- QoL score (*Section 10.1.7*)
- AEs (*Section 10.4.2*)
- Samples for anti-drug antibodies (*Section 10.1.9*)

For subjects using molgramostim in the Follow-up period:

- Serum pregnancy test (*Section 10.5*)
- Laboratory safety assessments (haematology and clinical chemistry), (*Section 10.4.6*).
- Administration of trial drug at the site (*Section 9.1.5*)
- Subject Diary Card (*Section 10.4.2*)
- Dispense trial drug (*Section 9.1.4*)
- Treatment compliance (*Section 9.5*)

7.2.1.12 24-Week Follow-up (Visit 11)

TIME WINDOW:

168 days (±14 days) after Week 24 (Visit 8)

ACTIVITIES AND ASSESSMENTS:

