9 TREATMENT OF SUBJECTS

9.1 Investigational Medicinal Products

9.1.1 Treatment Regimens

Subjects will be randomised to receive double-blind treatment for up to 24 weeks with either:

- inhaled molgramostim (300 µg) administered once daily,
- inhaled molgramostim (300 µg) and matching placebo administered intermittently (12 cycles of seven days molgramostim followed by seven days placebo; both administered once daily) or
- inhaled placebo administered once daily.

In the Follow-up period all subjects will receive treatment with inhaled molgramostim (300 µg) administered intermittently (12 or 24 cycles of seven days molgramostim followed by seven days off-treatment) for 24 or 48 weeks. For subjects who entered the Follow-up period before Amendment 11 was approved by the national authorities, treatment with molgramostim in the Follow-up period is not mandatory.

Treatment with molgramostim in the Follow-up period should be discontinued in case of disease worsening and/or safety concerns.

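### The exposure tables give elapsed days on regimen but not days on molgramostim, and the double-blind intervals stop short of the Visit 8 window

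*SAP*

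**What the plan says.** **Double-blind rule (SAP 5.3.9).** "exposure will be calculated as the number of days from the date of the first dose", ending at "to the date of Visit 8 or until date of discontinuation of double-blind Treatment, whichever occurs first". Nothing is subtracted for placebo weeks or interruptions.

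**Follow-up rule (SAP 5.3.9).** There are two rules. For early enrolment, "exposure for patients enrolled under protocol versions 1 through 3 will be calculated from start and stop dates" held in the concomitant medication pages. For versions 4 and 5, exposure "will be calculated from the date of Visit 8 to the date of Visit 11 or until discontinuation of treatment". Off-weeks are not subtracted.

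**Intervals (SAP 5.3.9).** The double-blind categories finish with "more than 16 to 20 weeks, and more than 20 to 24 weeks in the DB period". Follow-up is handled "similarly but in 4-weekly intervals in the FU period", with no upper end given.

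**Regimens (Protocol 9.1.1).** The intermittent arm receives "12 cycles of seven days molgramostim followed by seven days placebo; both administered once daily". Open-label treatment alternates seven days on drug with seven days off.

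**Visit timing.** Protocol 7.2.1.9 sets Visit 8 at "168 days (± 7 days) after Randomisation (Visit 2". The first dose is given at the Baseline visit after randomisation (Protocol 9.1.5).

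**Outputs (SAP Appendix 1).** Extent of exposure appears in Tables 14.2.6.1 to 14.2.6.6 and Listing 16.2.5.1.

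**The concern.** The trial compares two molgramostim regimens that differ in how many days the drug is given. A reader who turns to the extent-of-exposure table to see how much drug each arm received will find the same planned figure for once-daily and intermittent completers. No other planned output supplies the missing quantity. The compliance table divides returned empty vials by days in the trial and does not separate active from placebo vials. Neither cumulative dose nor days on drug is listed anywhere in Appendix 1.

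The interval problem is separate and simpler. The categories are meant to partition subjects by length of exposure, but a subject who completes treatment and attends Visit 8 late, within the permitted window, has no category. The counts and proportions in that part of the table need not then add up to the arm total.

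**Working it through.** **Inputs.** Cycle length and number of cycles (Protocol 9.1.1); Visit 8 window (Protocol 7.2.1.9); Visit 11 window, 168 ± 14 days after Visit 8 (Protocol 7.2.1.12); Day 1 is the day of first dose (SAP 5.3.2); interval limits (SAP 5.3.9).

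**1. Reproduce the nominal length.** 12 cycles × (7 + 7) days = 168 days = 24 weeks × 7. This matches the Visit 8 date.

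**2. Days on molgramostim, full course.**
- Once daily: 168 of 168 days, ratio 1.0.
- Intermittent: 12 × 7 = 84 of 168 days, ratio 168/84 = 2.0.
- Open-label, 24 weeks, versions 4 and 5: 12 × 7 = 84 of 168 days, ratio 2.0. This uses the 12 cycles in Protocol 9.1.1 and SAP 3.1. Protocol 7.1 instead says the cycle is repeated for 12 or 24 weeks; these passages must be reconciled, because expected drug days depend on them.

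**3. Early stops.** Ratio = elapsed days ÷ molgramostim days, with the active week first:
- day 7: 7/7 = 1.0
- day 21: 21/14 = 1.5
- day 77: 77/42 = 1.83
- day 161: 161/84 = 1.92

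The ratio is 2.0 at whole cycles and between 1 and 2 otherwise.

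**4. Visit 8 days outside every interval.** The window is day 161 to day 175, which is 175 − 161 + 1 = 15 days. The top interval ends at 24 × 7 = 168 days.
- Plain date difference: days 169 to 175 exceed 168, so 7 of 15 (46.7%).
- Inclusive count (+1): a visit on day 168 gives 169 days, so days 168 to 175 are outside, 8 of 15 (53.3%).

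SAP 5.3.9 does not say which count applies.

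**5. From days to subjects.** The documents give no distribution of visit dates, so the share of subjects is an assumption. It concerns those still on treatment at an in-window Visit 8. For normal visit dates truncated to the window, with SD 2 to 5 days:

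| Visit 8 dates | Date difference | Inclusive |
|---|---|---|
| Centred on day 168 | 40–45% | 55–60% |
| Centred 3 days early | 4–28% | 11–36% |
| Centred 3 days late | 64–89% | 72–96% |
| All exactly on day 168 | 0% | 100% |

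**6. Where the measure is used.** Adverse-event tables report numbers of subjects and events (SAP 5.3.11). The one planned rate model, number of WLLs, adjusts for length of follow-up, not exposure (SAP 5.3.7). No efficacy model contains exposure.

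**The case against.** The strongest reply is that the section concerns exposure to treatment, and treatment in the intermittent arm is the regimen itself, inhaled every day. On that reading 168 days is correct. The same definition also gives the placebo arm a sensible duration, whereas counting molgramostim days alone would give it zero. The tables are split by arm and the alternation is fixed by protocol, so a reader can halve the figure unaided. Follow-up subjects on the intermittent regimen also have their own analysis set. This stands: the planned measure is not wrong, and it should stay. It does not answer the point that the amount of drug received is reported nowhere, nor that early stops do not halve exactly.

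On the intervals, the reply is that no data are lost, because summary statistics and a by-subject listing are planned too. That is true, but the categories still fail to cover visits the protocol permits.

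A further fair objection concerns remedies based on vials. Vial counts go into a log kept at the site and kit labels into the diary card (Protocol 9.5). The documents do not show used vials recorded by kit in the database, so a count of active vials may not be available.

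**Conclusion.** The point holds as a small, descriptive gap with two parts. First, the only extent-of-exposure measure is elapsed time, which reads 168 days against 84 scheduled molgramostim days for a full intermittent course or a full 24-week open-label course under versions 4 and 5. Second, the double-blind intervals leave 7 of 15 permitted Visit 8 days (8 of 15 if inclusive) unclassified. The effect is confined to Tables 14.2.6.1 to 14.2.6.6.

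A reader might infer more, and the documents do not support it:
- *Exposure is overstated two-fold throughout.* The factor is relative to molgramostim days, is 2.0 only at whole cycles, and is not established for versions 1 to 3, where it depends on how cycles were entered in the start and stop dates.
- *About half of completers fit no interval.* That treats visit days as if they were subjects. The share could be anything from 0 to 100%.
- *Follow-up has the same ceiling.* None is stated. If follow-up intervals did end at 24 weeks, 14 of the 29 days in the Visit 11 window (15 of 29 if inclusive) would fall outside, but some subjects are followed for 48 weeks and the intervals may well run on.
- *Safety rates are biased.* No exposure-adjusted adverse-event rate is planned.

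**What to change.** In SAP 5.3.9:
- Label the existing measure *duration on regimen* and keep it.
- Add *days on molgramostim* beside it in the exposure tables. After unblinding, derive it from the regimen schedule and the first-dose and discontinuation dates already held, or from vial counts per kit if the database has them. State how days after the twelfth cycle are counted when Visit 8 is late.
- State whether the day count is inclusive.
- Make the last double-blind interval *more than 20 weeks*, and specify an open-ended top interval for follow-up.

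The cost is SAP wording and a little extra programming. The limitation is that schedule-derived days ignore missed doses, so the table should carry a footnote saying so.

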8.4.2 Discontinuation of Double-Blind Treatment

Subjects may be discontinued from double-blind treatment and assessments at any time, if deemed necessary by the investigator.

Potential reasons for discontinuation of double-blind treatment are:

- Lack of efficacy/worsening of disease
- Unacceptable AE

- Serious hypersensitivity reaction
- Pregnancy

Those who discontinue double-blind treatment will not automatically be withdrawn from the trial but will be encouraged to continue to follow the same visit schedule.

For example: if double-blind treatment is discontinued at Week 8 (Visit 4) the subject will be encouraged to attend the remaining visits in the Double-blind treatment period (Weeks 12, 16, 20 and 24) and continue into the Follow-up period. If the subject is reluctant to agree to 4-weekly visits, the investigator should request attendance at Week 24 (Visit 8) as a minimum.

The reason and date the subject is discontinued from double-blind treatment will be documented in the eCRF.

Subjects who fulfil the criteria for rescue treatment will be scheduled for a WLL as described in *Section 9.4*. Subjects receiving a WLL should continue Double-blind treatment and attend the remaining visits in the Double-blind treatment period and then continue into the Follow-up period.

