9.1.2 Identity of Investigational Medicinal Products

Each vial of molgramostim contains 250 µg/mL molgramostim in 1.2 mL solution. Matching placebo will contain the same constituents but without the active molgramostim.

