9.3 Blinding

All subjects will inhale IMP once daily during the Double-blind treatment period. Blinding will be ensured by the use of a matching placebo.

The packaging and labelling of the investigational products for the Double-blind treatment period will contain no evidence of their identity and it is not considered possible to differentiate between the investigational products solely by sensory evaluation.

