3 OVERALL STUDY DESIGN

3.1 Overview of Study Design

[figure not shown]
This is a parallel, double-blind, multicentre, randomised clinical trial in autoimmune pulmonary alveolar proteinosis subjects, where a planned total of 135 subjects (see section 3.2) are stratified according to whether or not a WLL has been conducted within 2 months prior to the Baseline (according to protocol version 4.0 and later versions), or whether or not

WLL was conducted between the screening visit and the randomization visit (according to protocol versions before version 4.0). Subjects will be randomised 1:1:1 to receive treatment for up to 24 weeks with either;

- 1) Inhaled molgramostim (300 µg) administered once daily,
- 2) Inhaled molgramostim (300 µg) and matching placebo administered intermittently (12 cycles of seven days molgramostim, seven days placebo; both administered once daily) or
- 3) Inhaled placebo administered once daily.

The trial includes two phases; a Double-blind treatment period consisting of up to eight trial visits (Screening, Baseline, and at Weeks 4, 8, 12, 16, 20 and 24 after randomisation) and a Follow-up period consisting of up to five trial visits (at Weeks 4, 12, 24, 36 and 48 post-treatment). During the follow-up period all subjects recruited under protocol version 4.0 or later versions will receive treatment with inhaled molgramostim (300 µg) administered once daily in an intermittent regimen for 24 weeks (12 cycles of seven days molgramostim, seven days off). Patients recruited under protocol version 2.0 were only to receive treatment in the follow-up period in case of worsening of aPAP, and patients recruited under protocol version 3.0 were treated (if needed) using the intermittent regimen for 24 weeks and according to investigator’s discretion for 24 additional weeks. Likewise, the 36 and 48-weeks post treatment visits are only applicable for subjects included before approval of protocol version 4.0.

Figure 1 Overall Trial Design

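### Compliance divides empty vials by days in the trial, which understates adherence in the 7-on/7-off follow-up and, in the double-blind period, mixes early stopping with adherence

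*SAP*

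**What the plan says.** SAP 5.3.9 gives one formula: "Compliance will be calculated as the total number of empty vials returned divided by the total number of days in the trial". The results are grouped as "90% or more; 80% or more; 70% or more; 50 to 69%; 49% or less". There is no follow-up version, no allowance for planned off-treatment days and no end point at treatment discontinuation. What counts as a day in the trial is not defined.

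The formula is meant for both periods. Protocol 9.5 assesses compliance by vial count in the double-blind and the follow-up period. SAP Appendix 1 lists Table 14.2.6.7 (Compliance) for three double-blind sets and three follow-up sets (FU-FAS, FU-MOL INT, FU-SAF).

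The dosing schedules differ:

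- Double-blind (Protocol 9.3): "All subjects will inhale IMP once daily during the Double-blind treatment period". The intermittent arm takes placebo in its off weeks.
- Follow-up (Protocol 9.1.1): "12 or 24 cycles of seven days molgramostim followed by seven days off-treatment) for 24 or 48 weeks". SAP 3.1 describes the same pattern for subjects under protocol version 4.0 or later: "12 cycles of seven days molgramostim, seven days off".
- Follow-up under early versions (SAP 3.1): "Patients recruited under protocol version 2.0 were only to receive treatment in the follow-up period in case of worsening of aPAP". Under version 3.0, treatment was given if needed.

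On stopping drug, Protocol 8.4.2 says: "Those who discontinue double-blind treatment will not automatically be withdrawn from the trial". Such subjects are asked to attend through Week 24.

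**The concern.** A compliance ratio should compare doses taken with doses due. Calendar days are a valid stand-in for doses due only if a dose is due on every one of those days. In follow-up that fails by design on every second week. In the double-blind period it fails for anyone who stops drug but stays under observation, which the protocol encourages.

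What is at stake is the adherence table in the two trial reports. The follow-up columns would make a group dosing exactly as instructed look poorly adherent. In the double-blind columns, if early stopping differs between arms, the table would show a compliance difference even where adherence while on drug was identical.

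**Working it through.** **Inputs**

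- Dose per vial (Protocol 9.1.2): "Each vial of molgramostim contains 250 µg/mL molgramostim in 1.2 mL solution". 250 × 1.2 = 300 µg, so one vial is one daily dose.
- Double-blind length: 168 days from randomisation to Visit 8 (Protocol 7.2.1.9).
- Follow-up to Visit 11: 168 days after Visit 8 (Protocol 7.2.1.12), which equals 12 cycles × 14 days. Scheduled dosing days: 12 × 7 = 84.
- Follow-up to Visit 13: 336 days, or 24 cycles. Scheduled dosing days: 24 × 7 = 168.

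The plan states no compliance figure to reproduce, so the check applies its formula to subjects who take every dose due to them.

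**Follow-up, days counted within the period**

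- 24 weeks: 84/168 = 50%.
- 48 weeks, treated throughout: 168/336 = 50%.
- Visit 11 at either end of its ±14-day window: 77/154 = 50% and 91/182 = 50%.
- 48 weeks with only 24 weeks treated: 84/336 = 25%. Untreated follow-up: 0%.
- One dose missed: 83/168 = 49.4%, against 83/84 = 98.8% of the doses due.

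On this reading nobody dosing as instructed can reach any band from 70% upward.

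**Follow-up, days counted over the whole trial**

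- Double-blind plus 24-week follow-up: (168 + 84)/(168 + 168) = 252/336 = 75%.
- With 14 screening days added: 252/350 = 72%.

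**Double-blind, subject stays on drug**

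168/168 = 100% in all three arms, counting days from Baseline to Visit 8.

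**Double-blind, every dose taken until stopping, then observed to Week 24**

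| Stop at | Vials / days | SAP formula | Vials / doses due to the stop |
|---|---|---|---|
| Week 4 | 28/168 | 16.7% | 28/28 = 100% |
| Week 8 | 56/168 | 33.3% | 56/56 = 100% |
| Week 12 | 84/168 | 50.0% | 84/84 = 100% |
| Week 16 | 112/168 | 66.7% | 112/112 = 100% |
| Week 20 | 140/168 | 83.3% | 140/140 = 100% |

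**Comparison within the same section.** SAP 5.3.9 ends double-blind exposure at Visit 8 or at treatment discontinuation, whichever comes first. The compliance denominator has no such end point. The two definitions therefore treat the same subject differently.

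**The case against.** The best defence is that little depends on this number. Neither per-protocol definition (Protocol 12.1.1, SAP 4) states a compliance threshold. The main analyses of (A-a)DO₂, 6MWD and SGRQ use data regardless of adherence, and follow-up is reported descriptively. This stands, and it limits the weight of the point. It does not make the table right.

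Second, vials over days in the trial can be read as a measure of treatment actually received, in keeping with the de-facto approach in SAP 5.3.6. Early stopping is also visible elsewhere: in exposure by 4-week intervals, in disposition (SAP 5.3.5), in Table 14.1.7 and in the compliance listing itself. This stands in part. Discontinuation is not hidden, so the double-blind limb is the smaller one. But exposure already serves that purpose, and a listing does not correct the summary table.

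Third, 50% depends on how days in the trial is read. That is true. The separate follow-up columns favour the within-period reading, but the SAP does not settle it. No reading considered here gives a perfect follow-up adherer 100%.

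Some stronger inferences should be resisted:

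- *That early stoppers are classed as non-compliant.* The SAP sets no such cut-off, and the effect is graded.
- *That 49.4% falls in no band.* The bands are in whole percentages, and 49.4% rounds to 49%. A gap exists only if unrounded values are banded, which the SAP does not say. What can be said is that the rounding rule is missing and that the top three bands are cumulative as written while the lower two are exclusive.

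**Conclusion.** The point holds for the follow-up denominator and, to a lesser degree, for early stoppers in the double-blind period. Perfect follow-up adherence is reported as 50% (within-period days) or about 72 to 75% (whole-trial days). In the double-blind period the formula is correct for subjects who stay on drug in every arm. It falls short only for those who stop and remain under observation, from 16.7% for a Week 4 stop to 83.3% for a Week 20 stop.

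This assumes one vial per dose, visits on nominal days and every used vial returned. It takes the cycle counts from Protocol 9.1.1 and SAP 3.1. Protocol 7.1 instead says the cycle is repeated for 12 or 24 weeks, and these passages must be reconciled before a schedule is programmed.

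A reader might infer that the double-blind adherence results, the per-protocol set or the efficacy conclusions are unsafe. The documents do not support that. No test, estimate or stated analysis-set rule uses compliance. What is wrong is a descriptive adherence table, chiefly its follow-up columns.

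**What to change.** Redefine compliance in SAP 5.3.9 separately for each period:

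- **Ratio:** empty vials returned divided by scheduled dosing days.
- **Denominator window:** from the first dose in the period to the recorded treatment-discontinuation date or the end of the period, whichever is earlier. It should not end at the last dose taken, because a subject who silently stopped would then score as fully compliant.
- **Scheduled days:** every day in the double-blind period; only the days of on-treatment weeks in follow-up.
- **Early-version follow-up subjects without mandatory treatment:** limit the denominator to their recorded treatment start and stop dates, or list them without summarising. SAP 5.3.9 already uses such dates for exposure under versions 1 through 3.
- **Bands:** exclusive and contiguous, namely ≥90, 80 to <90, 70 to <80, 50 to <70 and <50%.

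Discontinuation needs no new output, since it is already reported.

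The cost is a change of SAP wording and one derivation. First-dose and discontinuation dates are recorded, and vial counts are already needed for the present formula. One limit remains: the weekly kit-label check in Protocol 9.5 covers only the double-blind period, so follow-up on-weeks would have to be derived from the planned alternation and not from recorded use. The SAP should say so.
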